7.0 Data and Specimen Banking* N/A

8.0 Sharing of Results with Subjects*

8.1 Results will not be shared.

9.0 Study Timelines*

- An individual study subject's participation in the study should last approximately 2 weeks total.
- All study subjects should be enrolled within 2 years of study start.
- The study should be completed within 3 years of study start.

10.0 Inclusion and Exclusion Criteria*

- 10.1 Potential subjects will be identified by reviewing the surgery schedule in Epic and will be recruited from the Surgery Unit pre-op area prior to their surgery.
- 10.2 Inclusion criteria: Patients 10 21 years of age, with American Society of Anesthesiologists physical status I and II, undergoing elective anterior cruciate ligament reconstruction.
- 10.3 Exclusion criteria: Patients will not participate in the study if any of the following apply to them:
 - They are unable or unwilling to take part in the study
 - History of allergy to any of the medications administered for the nerve block
 - Contraindication to peripheral nerve block
 - Patients who are unable to understand instructions or questions related to the study or the families required language interpretation.
 - Patients who consume opioid medications for more than three days per week for more than a month prior to surgery.
- 10.4 We are including children, and will not include:
 - Adults unable to consent
 - Pregnant women
 - Prisoners

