3.0 Background

- 3.1 Anterior cruciate ligament reconstruction is one of the most common orthopedic surgical procedures performed on an outpatient basis.1 The ability to effectively discharge these patients is primarily determined by the efficacy of postoperative pain control. Regional anesthetic techniques are commonly used to provide postoperative analgesia as they provider superior analgesia when compared to opioids and have also been shown to facilitate same day, outpatient discharge home.2 Various regional techniques have been used, generally combining blockade of the femoral and sciatic nerve to provide analgesia of the knee and surrounding structures. Performance of the sciatic nerve block can be technically challenging and time consuming. One alternative to sciatic nerve block is infiltration of the posterior knee capsule (IPACK) under ultrasound guidance. Results with IPACK in adults for posterior knee joint analgesia in patients undergoing total knee arthroplasty have been comparable to sciatic nerve block. Furthermore, IPACK is technically less challenging as it is only infiltration of the knee capsule below the division of the sciatic nerve, without targeting for nerves, and is not associated with motor block.3
- 3.2 The aim of the current study is to determine if the analgesic efficacy of IPACK is similar to sciatic nerve block thereby reducing the side effects involved with sciatic nerve block as well as the technical challenges of performing the block.

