5.0 Study Intervention/Investigational Agent

5.1 Study subjects will receive up to 20 mL of 0.5% ropivacaine with epinephrine 1:200,000 and 0.2 mg/ml of dexamethasone for FNB and up to 20 mL of 0.5% ropivacaine with epinephrine 1:200,000 and 0.2 mg/ml of dexamethasone for sciatic nerve block under ultrasound guidance or posterior knee capsular infiltration under ultrasound guidance (IPACK), the total dose not to exceed 3 mg/kg of ropivacaine.

5.2 Both the FNB and sciatic nerve blocks are considered standard of care at NCH. The IPACK is not currently performed at NCH.

6.0 **Procedures Involved***

- Following informed consent, patients will be randomized into one of 6.1 the two groups. Intraoperative anesthetic care will not vary from our usual practice. Patients requiring preoperative anxiolysis will receive oral midazolam (0.3-0.5 mg/kg, maximum 20 mg) 30 minutes prior surgery or intravenous midazolam (0.05 mg/kg, maximum 2 mg) prior to transport to the operating room. Standard American Society of Anesthesiologists' monitors will be placed. Once in the operating room, anesthesia will be induced by the intravenous or inhalational route as clinically indicated. All subjects will receive propofol (2-3 mg/kg) and fentanyl (2µg/kg). Following the induction of anesthesia, an appropriately sized laryngeal mask airway (LMA) will be placed. After the regional anesthesia time out, patients will receive the block based on the group assigned from a randomization list created by www.sealedenvelope.com. The time from the initiation of the timeout for the block until the patient has been returned to the surgical position will be noted.
- 6.2 The following demographic and surgical parameters will also be collected and recorded: patient age, gender, race/ethnicity, height, weight, ASA status, primary diagnosis, list of comorbidities, procedure date and duration, admission status, intraoperative medications and postoperative medications, PACU arrival and discharge times, discharge destination, pain scores (including recorded time), regional anesthetic time and dose, postoperative opioids consumed and time of hospital admission and discharge.

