17.0 Data Management* and Confidentiality

17.1 Continuous outcomes will be compared between groups using 2sample t-test or rank-sum tests according to the normality of the distribution (checked by the Shapiro-Wilk test). Categorical outcomes will be compared between groups using Chi-square or Fisher's exact tests, according to cell size.

- 17.2 Research records will be stored in a locked cabinet and password protected computer. Only certified research personnel will be given access to identifiable subject information
- 17.3 Following publication of study results, research records will be stored for a period of 3-5 years and then will be destroyed by placing in a secure shredding bin.

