- 5.0 Check each box that describes steps that will be taken to safeguard the confidentiality of information collected for this research:

 □ Research records will be stored in a locked cabinet in a secure location
 □ Research records will be stored in a password-protected computer file
 □ The list linking the assigned code number to the individual subject will be maintained separately from the other research data
 □ Only certified research personnel will be given access to identifiable subject information
- 6.0 Describe the provisions included in the protocol to protect the privacy interests of subjects, where "privacy interests" refer to the interest of individuals in being left alone, limiting access to them, and limiting access to their information. (This is not the same provision to maintain the confidentiality of data.)

Subjects and their families will be approached about the study and consented in a private room in the pre-op area by a member of the research team. The information collected will be limited to that which is required to achieve the objectives of the study and will not be shared with anyone not directly involved in the study. Subjects will be informed of their right to refuse to participate.

Confidential Health Information

1.0 Please mark all categories that reflect the nature of health information to be accessed and used as part of this research.

- Demographics (age, gender, educational level)
- \boxtimes Diagnosis
- □ Laboratory reports
- □ Radiology reports
- □ Discharge summaries
- ☑ Procedures/Treatments received
- Dates related to course of treatment (admission, surgery, discharge)
- \Box Billing information
- ⊠ Names of drugs and/or devices used as part of treatment
- \Box Location of treatment
- \Box Name of treatment provider
- □ Surgical reports
- \boxtimes Other information related to course of treatment
- □ None
- 2.0 Please discuss why it is necessary to access and review the health information noted in your response above.It is necessary to meet the objectives of the study and to analyze the data.
- 3.0 Is the health information to be accessed and reviewed the minimal necessary to achieve the goals of this research? \boxtimes Yes \square No
- 4.0 Will it be necessary to record information of a sensitive nature? \Box Yes \boxtimes No
- 5.0 Do you plan to obtain a federally-issued Certificate of Confidentiality as a means of protecting the confidentiality of the information collected? \Box Yes \boxtimes No

References:

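### Any elective ACL reconstruction is eligible, but operation type is neither listed as study data nor adjusted for: avoidable imprecision, not bias

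*Combined protocol and SAP*

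**What the plan says.** - **Eligibility (10.2 to 10.4).** Patients qualify if they are "undergoing elective anterior cruciate ligament reconstruction", subject to age and ASA status. The exclusions concern the patient or the block, for example "Contraindication to peripheral nerve block". None concerns graft source, revision surgery or concomitant procedures.
- **Data to be recorded (6.2).** The entries that bear on the operation are in the run "primary diagnosis, list of comorbidities, procedure date and duration, admission status". Graft source, primary or revision status and added meniscal or ligament work are not named.
- **Allocation (6.1).** "patients will receive the block based on the group assigned from a randomization list created by www.sealedenvelope.com". No stratification factor is given.
- **Analysis (17.1).** "Continuous outcomes will be compared between groups using 2sample t-test or rank-sum tests according to the normality of the distribution". No covariate is named.
- **Health-information checklist (27.0, under Confidential Health Information).** The broad category "Procedures/Treatments received" is ticked, as is a catch-all for other treatment information. The box for surgical reports is not ticked.
- **Sample size (12.2).** The comparison is maximal pain on POD0, with a 1-point non-inferiority margin, SD 1.1, a one-sided test at 95% confidence, 90% power with at least 22 per group, and 50 enrolled.

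**The concern.** How much surgery is done, and where, is a plausible source of variation in postoperative pain. The plan leaves that variation open at entry, does not ask for it to be recorded, and does not use it in the analysis. In 50 patients the arms can differ by chance in their mix of operations. A reader of the results, working from the listed data, could not tell whether they did.

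At stake are the credibility and precision of a narrow claim, that IPACK is at most 1 point worse on maximal POD0 pain. A chance shift of a few tenths of a point matters on that scale. A prognostic variable that is never collected also cannot be used later to sharpen the estimate.

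**Working it through.** **Inputs from the documents (12.2):** margin 1 point, SD 1.1, one-sided alpha 0.05, 22 per group needed, 50 enrolled (25 per group if allocation is 1:1, which is implied but not stated).

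**Assumptions (the documents give no figures):** one binary surgical factor with prevalence *p* of 20–50% and an effect on maximal pain *δ* of 0.5–2 points.

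**1. The plan's own figure.** With a true difference of 0, the normal approximation is n = 2(1.645 + 1.282)² × 1.1² / 1² = 20.7, so 21 per group. For the exact t-test the noncentrality is 1/(1.1√(2/n)). Power is 89.4% at 21 and 90.7% at 22. The stated 22 reproduces. At 25 per group power is 93.6%.

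**2. How often the arms differ by chance.** Take two independent Bin(25, *p*) counts. A gap of 5 or more patients is 20 percentage points or more.

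| *p* | SD of difference, √(2p(1−p)/25) | P(gap ≥ 20 points), either direction | Favouring IPACK |
|---|---|---|---|
| 20% | 0.113 | 0.11 | 0.055 |
| 30% | 0.130 | 0.16 | 0.08 |
| 50% | 0.141 | 0.20 | 0.10 |

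**3. What such a gap does.** Shift = *δ* × 0.20. The last two columns condition on that gap. They use 25 per group and hold the SD at 1.1, so they are illustrative.

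| *δ* | Shift (points) | Power if the shift is against IPACK | False non-inferiority rate if the shift favours IPACK and the true difference is 1 |
|---|---|---|---|
| 0.5 | 0.1 | 88.6% | 9.2% |
| 1 | 0.2 | 81.3% | 15.6% |
| 2 | 0.4 | 60.1% | 35.3% |

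Without a shift these two rates are 93.6% and 5%.

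**4. Effect on power over all allocations.** If 1.1 is the SD within operation type, the total SD is √(1.1² + p(1−p)δ²). At *p* = 50%:

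| *δ* | Total SD | Exact-t power, 22 per arm | Exact-t power, 25 per arm |
|---|---|---|---|
| 0 | 1.10 | 0.91 | 0.94 |
| 1 | 1.21 | 0.85 | 0.89 |
| 2 | 1.49 | 0.71 | 0.76 |

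If 1.1 is already the total SD, power does not fall below plan. The residual SD after adjustment would be √(1.1² − 0.25δ²), which is 0.98 for *δ* = 1, so adjustment would gain precision. For *δ* = 2 it would be only 0.46, so under that reading the top of the assumed range fits poorly with the planned SD.

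**5. Steps 3 and 4 are one quantity.** For *δ* = 1, *p* = 50% and 25 per arm, the variance of the difference is 1.1² × 2/25 = 0.0968 from other sources, plus (1 × 0.141)² = 0.0200 from the surgical factor. The sum, 0.1168, equals 1.46 × 2/25, where 1.46 is the squared total SD (1.21 + 0.25). The chance shift and the wider SD are two views of the same component and must not be added together.

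**The case against.** The strongest reply is that randomisation already deals with this. Chance imbalance in any prognostic factor is part of the t-test's standard error, and the unconditional one-sided error rate stays at 5%. The same could be said of any unrecorded covariate in any small trial, and broad eligibility is a legitimate choice. All of that stands. The conditional figures in step 3 describe unlucky allocations, not the test's operating characteristics.

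Three stronger readings are tempting, and the documents do not support them.

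- **That the comparison is biased.** Allocation comes from "the group assigned from a randomization list created by www.sealedenvelope.com". The absence of a stratification factor does not bias the result, and the 0.1–0.4 point shift is chance.
- **That operation type could never be seen or corrected.** The checklist ticks "Procedures/Treatments received", and 6.2 records primary diagnosis and procedure duration. Access to the information is not ruled out. But none of these entries makes graft source, revision status or concomitant work a study variable.
- **That the documents show harvest-site or added-procedure pain to lie outside what IPACK covers.** Section 3.1 says "it is only infiltration of the knee capsule below the division of the sciatic nerve" to explain why the technique is easier. It does not map sources of pain, both arms also receive FNB (6.3), and no section gives a pain effect for graft or added surgery.

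The magnitudes also depend on assumptions. At 20% prevalence and a 0.5-point effect the issue is small. Whether 1.1 includes variation between operations is not stated. Section 12.2 calls it simply the SD of pain scores, and the reference list identifies its source as a trial in total knee arthroplasty, so neither reading can be excluded.

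What remains is that the listed data would not reveal an imbalance and the planned test could not adjust for one, although both are cheap to put right.

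**Conclusion.** The point holds as a matter of precision and transparency, not validity. Operation type is open at entry, absent from the listed study data and absent from the analysis. Under the assumed prevalence of 20–50%, there is an 11–20% chance that the arms differ by 20 percentage points or more on one surgical factor, and a 5.5–10% chance that they do so in the direction that flatters IPACK. Under the assumed effect of 0.5–2 points, a 20-point gap moves the estimate by 0.1–0.4 points, or 10–40% of the margin.

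Power is lost relative to plan only if the SD of 1.1 excludes this variation. At 50% prevalence and effects of 1–2 points, it is then 0.85–0.71 at 22 per arm or 0.89–0.76 at 25. The figure for 25 assumes that nobody is lost, although 12.2 holds the extra patients partly in reserve for exclusions and missing data. The stated sample size is correct on its own inputs. This is a worthwhile, low-cost improvement, and it does not require narrower eligibility.

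**What to change.** 1. Add three fields to 6.2: graft source, primary or revision status, and concomitant meniscal or ligament procedures. If the operative report is the source, update the health-information checklist in 27.0, where surgical reports are not ticked.
2. Report the three fields by arm.
3. In 17.1, pre-specify a comparison of maximal POD0 pain adjusted for graft source, for example a linear model with terms for arm and graft source. Read the upper one-sided 95% confidence bound for IPACK minus sciatic against the 1-point margin. Fix the graft categories in advance. Add concomitant meniscal repair as a sensitivity analysis.
4. Optionally, stratify the randomisation list by graft source (for example autograft versus allograft), if it is known before allocation. The documents do not say whether it is, and in 50 patients recording and adjustment are the more important steps.

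The cost is three data fields, one covariate and possibly one checklist change, with slightly more allocation administration if the list is stratified. No extra patients or procedures are needed.

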11.0 Vulnerable Populations*

11.1 This study presents no more than minimal risk as it involves regional nerve blocks which are used routinely as standard of care by the anesthesiologists at this institution.

12.0 Local Number of Subjects

- 12.1 50
- 12.2 Sample size will be determined according to previous studies in adults. Abdallah et al. described the non-inferiority of the IPACK block over 24 hours postoperatively, while Kim et al. described superiority of IPACK with respect to pain scores at rest and ambulation, as well as opioid consumption, over postoperative days 0-1. With the greatest pain observed on POD0, our study will be powered for comparing the maximal pain score on POD0 between the 2 groups. Based on the data presented by Abdallah et al., we anticipate that pain scores over POD0 would differ by no more than 1 point between the groups, on a 0-10 scale. Based on the data presented by Kim et al., we hypothesize a standard deviation of pain scores of 1.1. Following Abdallah et al, our study will be powered for a test of IPACK non-inferiority, such that the null hypothesis will

be rejected if pain scores in the IPACK group are >1 point greater than in the control group. Under these assumptions, an unpaired onetailed t-test would attain 90% power for rejecting the null hypothesis at a 95% confidence level when at least 22 patients are enrolled in each group. We propose enrolling a total of 50 patients to account for non-normal distribution of the primary outcome; protocol violations resulting in subject exclusion; and missing data.

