1.0 Study Summary

Study Title	Comparison of postoperative analgesic efficacy of femoral	
	nerve block with IPACK versus femoral and popliteal sciatic	
	nerve block in patients undergoing arthroscopic anterior	
	cruciate ligament reconstruction.	
Study Design	Prospective study	
Primary Objective	The primary objective of the study is to compare the	
	analgesic efficacy of FNB with IPACK versus FNB with	
	sciatic nerve block in patients undergoing ACL repair by	
	monitoring postoperative pain scores.	
Secondary	The secondary objective is to show a decreased incidence of	
Objective(s)	adverse effects including motor blockade with IPACK	
	compared to sciatic nerve block and to demonstrate that it is	
	technically less challenging by showing a decreased time	
	required for performance of the block.	
Research	Patients will receive up to 20 mL of 0.5 % ropivacaine with	
Intervention(s)/	epinephrine 1:200,000 and 0.2 mg/ml of dexamethasone for	
Investigational	FNB-AC and up to 20 mL of 0.5% ropivacaine with	
Agent(s)	epinephrine 1:200,000 and 0.2 mg/ml of dexamethasone for	
	sciatic nerve block or posterior knee capsular infiltration.	
IND/IDE #	N/A	
Study Population	Patients undergoing elective anterior cruciate ligament	
	reconstruction.	
Sample Size	50	
Study Duration for	Total of 2 weeks.	
individual		
participants		
Study Specific	IPACK – infiltration of the posterior knee capsule	
Abbreviations/	FNB - Femoral nerve block	
Definitions	PACU – post-anesthesia care unit	
	POD – post-op day	

2.0 **Objectives**

- 2.1 The primary objective of the study is to compare the analgesic efficacy of FNB with IPACK versus FNB with sciatic nerve block in patients undergoing ACL repair by monitoring postoperative pain scores.
- 2.2 The secondary objective is to show a decreased incidence of adverse effects including motor blockade with IPACK compared to sciatic nerve block and to demonstrate that it is technically less challenging by showing a decreased time required for performance of the block.
- 2.3 We hypothesize that FNB with IPACK provides the same analgesic efficacy as FNB with sciatic block while avoiding the motor blockade associated with sciatic nerve block.

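### The non-inferiority rule in section 12.2 is reversed: it rejects the null when IPACK is more than 1 point worse, and section 17.1 supplies no margin or confidence limit to correct it

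*Combined protocol and SAP*

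**What the plan says.** Section 2.3 sets the aim: "We hypothesize that FNB with IPACK provides the same analgesic efficacy as FNB with sciatic block". Section 12.2 turns this into a test on the maximal pain score on POD0. It states that "our study will be powered for a test of IPACK non-inferiority, such that the null hypothesis will" and, continuing the sentence, "be rejected if pain scores in the IPACK group are >1 point greater than in the control group". The same section gives the design values: "we anticipate that pain scores over POD0 would differ by no more than 1 point between the groups, on a 0-10 scale", "we hypothesize a standard deviation of pain scores of 1.1", and "an unpaired onetailed t-test would attain 90% power for rejecting the null hypothesis at a 95% confidence level" with at least 22 patients per group. Planned enrolment is 50.

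The only analysis text is section 17.1: "Continuous outcomes will be compared between groups using 2sample t-test or rank-sum tests according to the normality of the distribution", with normality checked by the Shapiro-Wilk test. That line covers all continuous outcomes alike. It does not single out the primary outcome and gives no margin, sidedness, confidence limit or non-inferiority criterion.

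**The concern.** In a non-inferiority test the null hypothesis is that the new treatment is worse by the margin or more. It is rejected, and non-inferiority concluded, when the data exclude a deficit that large. Section 12.2 rejects in the opposite direction: large excess pain under IPACK leads to rejection. Rejecting on that basis shows that IPACK is inferior, which contradicts the purpose named earlier in the same sentence.

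This is the only decision rule for the one comparison the trial is powered on. An analyst who follows it literally tests for inferiority. An analyst who turns to section 17.1 is likely to run a test of zero difference, and a non-significant result from that test could be read as similar efficacy. Neither route delivers the intended claim with its error rate held at 5%. If the rule is corrected only after data are seen, the success criterion becomes post hoc.

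**Working it through.** **Inputs.** From section 12.2: margin 1 point, SD 1.1, unpaired one-tailed t-test, 95% confidence level (one-sided alpha 0.05), 22 per group. The true difference behind the 90% power is not stated. I take it as 0, which fits the hypothesis in section 2.3. Write D for the true mean difference, IPACK minus sciatic, and d for the observed one.

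**Common quantities at 22 per group.**
- SE = 1.1 × √(2/22) = 0.332
- df = 2 × 22 − 2 = 42
- one-sided 5% critical t = 1.682

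**Step 1: reproduce the plan's figure.** The correctly directed test rejects D ≥ 1 when (d − 1)/SE < −1.682. Its power comes from the noncentral t with noncentrality (D − 1)/SE, which at D = 0 is −1/0.332 = −3.02. Power is 90.7% with 22 per group and 89.4% with 21. So 22 is the smallest group size reaching 90%, and the plan's figure reproduces.

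This does not show which rule was meant. A one-sided test of zero difference, powered to detect a true 1-point difference, has noncentrality +3.02 and by symmetry the same 90.7%.

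**Step 2: compare the two directions.**
- Correct rule: the observed difference must be below 1 − 1.682 × 0.332 = 0.44.
- Literal rule, as a one-tailed t-test against +1: reject when (d − 1)/SE > 1.682, so the observed difference must exceed 1 + 1.682 × 0.332 = 1.56.

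Probability of rejecting the null, 22 per group, SD 1.1:

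| True difference D | Correct rule | Literal rule |
|---|---|---|
| 0 | 90.7% | 0.0002% |
| 0.5 | 43.6% | 0.1% |
| 1 | 5.0% | 5.0% |
| 1.5 | 0.1% | 43.6% |
| 2 | about 0% | 90.7% |

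The columns mirror each other about D = 1. Simulation with 400,000 trials per scenario agreed: 90.7% for the correct rule at 0, and 5.0% and 43.6% for the literal rule at 1 and 1.5.

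**Step 3: does section 17.1 repair it?** Suppose its t-test is run against zero difference and non-significance is taken as similarity. Section 17.1 states neither alpha nor sidedness, so both are assumed here. At a true deficit of 1 point, the chance of a non-significant result is:

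| | 22 per group | 25 per group |
|---|---|---|
| Two-sided 0.05 | 16.2% | 11.7% |
| One-sided 0.05 | 9.3% | 6.4% |
| Correct non-inferiority rule (false claim) | 5.0% | 5.0% |

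The fallback rate also depends on the SD. As an illustration only, at an assumed SD of 2.0 (not in the documents) the two-sided figure at 22 per group is 63%. Noisier data make non-significance easier to reach, whereas they make the correct non-inferiority criterion harder to meet.

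**The case against.** The strongest reply is that this is a slip of wording and the intended test can be recovered. Section 12.2 names non-inferiority, gives the 1-point figure, a one-tailed t-test and a 95% level, and its sample size matches the correctly directed test. Section 17.1 is a generic line, and a two-sample t-test can be run against a shifted null of 1. It is true that the aim is clear and that the margin and level appear in 12.2. But the direction is stated only once and is stated wrongly, and the sample size cannot settle it, because a one-sided test of zero difference needs the same number.

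Three narrower points stand as qualifications.

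- **The literal-rule rates belong to one reading.** If the rule means a point estimate above 1, equal blocks reject 0.1% of the time and a true 1-point deficit 50%. If it means a one-sided test of zero difference, the figures are 5% and 90.7%. None of these readings is a valid non-inferiority rule.
- **The fallback harm is conditional.** No passage says non-significance will be read as non-inferiority, and the rates are lower if all 50 patients are evaluable (Step 3).
- **The 90% power is for the t-test.** With normal data, simulation puts the rank-sum version at about 89% with 22 per group and about 93% with 25, so the planned 50 covers it. The rank-sum branch also targets a location shift rather than a mean. The Shapiro-Wilk switch in 17.1 already creates that ambiguity.

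**Conclusion.** The concern holds. The decision rule in section 12.2 points the wrong way for the trial's only powered comparison, and nothing elsewhere in the document states it correctly. Taken literally as a t-test, it would almost never reject if the blocks are equal, and would reject most often when IPACK is clearly worse. The sample size is not in error: 22 per group gives 90.7% power for the correct test, assuming SD 1.1, one-sided alpha 0.05 and a true difference of 0. The size of the fallback risk rests on the assumed sidedness and alpha of section 17.1. The reversal itself rests on the text alone and needs no assumption. It must be corrected before the data are analysed.

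**What to change.** In section 12.2, replace the rejection sentence with:

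> H0: mean maximal POD0 pain, IPACK minus sciatic, is 1 point or more. H1: it is less than 1 point. Non-inferiority is concluded if the upper one-sided 95% confidence limit for the difference is below 1.

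State there that the 90% power assumes a true difference of 0. Optionally, report power at other values with 22 per group: 71.9% at 0.25 and 43.6% at 0.5.

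In section 17.1, name maximal POD0 pain as the primary outcome and repeat the rule. If the rank-sum branch is used, compare the upper one-sided 95% confidence limit for the location shift (for example Hodges-Lehmann) with the same 1-point margin. Add that a non-significant difference test will not be read as non-inferiority.

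The cost is one or two sentences in 12.2 and about two in 17.1. No patients are added, and the 22 per group and planned 50 stand. The only downside is that the zero-difference assumption behind the power becomes visible.

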14.0 Withdrawal of Subjects*

14.1 Patients experiencing severe pain with VAS scores >7 at the surgical site will be considered as failed FNB or sciatic nerve block and will be withdrawn from the study.

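### A non-inferiority comparison that anticipates post-randomisation exclusions, withdraws patients on the pain outcome itself, and names no analysis population

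*Combined protocol and SAP*

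**What the plan says.** Section 12.2 of the combined protocol and SAP sets the design: "our study will be powered for a test of IPACK non-inferiority", and "our study will be powered for comparing the maximal pain score on POD0 between the 2 groups". The margin is 1 point and the SD is 1.1. The test is a one-tailed t-test at 95% confidence, needing 22 per group. Enrolment is then set at 50 for three reasons together: non-normality, "protocol violations resulting in subject exclusion; and missing data".

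Sections 6.5 and 14.1 add a withdrawal rule based on pain. Patients with VAS above 7 at the surgical site "will be considered as failed FNB or sciatic nerve block and will be withdrawn from the study".

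Section 17.1 gives the choice of tests (t or rank-sum, chi-square or Fisher) and nothing about who is analysed. No section defines an as-randomised or a per-protocol set, lists the violations that exclude, says who judges them, or says whether a withdrawn patient's scores are used.

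On experience with the technique, section 5.2 says "The IPACK is not currently performed at NCH", whereas femoral and sciatic blocks are standard of care at the site. Section 3.1 describes sciatic block as technically demanding and IPACK as the easier of the two.

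**The concern.** Randomisation follows consent, and the block is given after induction (section 6.1). Any violation in giving the block, and any VAS above 7, therefore arises after randomisation. Dropping such patients breaks the randomised comparison. In a non-inferiority test, losing the worst outcomes from the new-treatment arm moves the estimate towards zero, which is the direction that produces a positive claim.

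The VAS >7 rule is the more direct problem because it selects on the variable being analysed: a patient withdrawn on POD0 has, by definition, one of the highest maximal POD0 scores. With about 25 patients per arm, two or three such decisions could settle the result. The plan does not fix those decisions in advance, and section 6.5 states blinding only for the postoperative nursing staff.

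**Working it through.** **1. The plan's own figure.** Inputs from section 12.2: margin 1, SD 1.1, true difference 0, one-sided 5%, power 90%. The rejection rule there is worded backwards. It is read here as a null hypothesis that IPACK is worse by 1 point or more.

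Normal approximation: n = 2 × 1.1² × (1.645 + 1.282)² / 1² = 2.42 × 8.57 = 20.7, so 21 per group. The exact t calculation gives power 0.894 at 21 and 0.907 at 22, so the stated 22 per group is reproduced. At 25 per group, power is 0.936. The allowance is 50 − 44 = 6 patients (6/50 = 12%), across both arms and all three reasons.

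**2. Excluding worse-off IPACK patients.** The documents give no failure rate and no excess pain for failed blocks, so both are assumed. Let a fraction f of IPACK patients score s points higher, and let the all-randomised difference be exactly 1 (truly inferior at the margin). If those patients are dropped, the expected difference becomes 1 − f × s. Simulation: 25 per arm, SD 1.1, one-sided 5% t-test against the margin, 40,000 runs, failures occurring at rates of 4%, 8% and 12%.

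| IPACK patients excluded (average, of 25) | Expected difference after exclusion, s = 2 / 3 / 4 | False non-inferiority after exclusion | All kept |
|---|---|---|---|
| 1 | 0.92 / 0.88 / 0.84 | 8% / 10% / 13% | 5-6% |
| 2 | 0.84 / 0.76 / 0.68 | 13% / 18% / 26% | 5-7% |
| 3 | 0.76 / 0.64 / 0.52 | 18% / 29% / 43% | 5-7% |

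Hand check of the last cell: SE = 1.1 × √(1/22 + 1/25) = 0.322; (1 − 0.52)/0.322 = 1.49; 1.49 − 1.68 (t critical value, 45 df) = −0.19, a probability of about 43%.

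**3. The VAS >7 rule.** The documents give no expected mean, so control means of 4 to 5 are assumed, with a true difference of 1 point. The SD of 2.0 is also an assumption.

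| Rule removes VAS >7 from | SD 1.1 | SD 2.0 |
|---|---|---|
| Both arms | 8-23% false non-inferiority | 14-22% |
| Control arm only | 3-5% | 0.3-2% |

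The direction depends on whom the rule covers.

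**4. Price of keeping everyone.** Suppose IPACK patients whose block works match control exactly, and failures are retained. The true difference is f × s and power falls from 94%:
- 1 of 25 at +2: difference 0.08, power about 89%
- 8% at +4: difference 0.32, power about 56%
- 12% at +4: difference 0.48, power about 38%

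**The case against.** The best defence is that the exclusion phrase is one of three reasons for a larger enrolment, not an analysis rule. That is right as far as it goes. A reader might infer that the plan orders failed or abandoned IPACK blocks to be dropped, or that section 17.1 compares only the patients who remain. The documents say neither. No section calls an incomplete, extra or changed block a protocol violation, and section 17.1 is silent on population.

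The direction is also contestable. Lack of local experience with IPACK points one way, and section 3.1's account of sciatic block as the harder technique points the other. The withdrawal rule names femoral and sciatic failures, not IPACK. Since both groups receive a femoral block, its reach into the IPACK arm is unclear.

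Extreme scenarios can be built: with 20-25% of IPACK blocks failing at 4-5 points worse and all excluded, non-inferiority is declared about 90% of the time at a true difference equal to the margin. That needs 5 or 6 of 25 failures, all in one arm. It would use nearly the whole allowance and leave that arm below 22. Nothing in the documents supports those inputs.

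What the defence does not supply is any statement that patients are kept as randomised. Exclusion is expected, withdrawal depends on the outcome, and no analysis set offsets either.

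**Conclusion.** The point holds as a defect in the analysis population, not in the sample size, which is correct on its own assumptions. Followed as written, the plan allows post-randomisation removal of patients, partly on the primary outcome, with no rule that protects the randomised comparison.

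If the removed patients are mainly IPACK patients with worse pain, losing one to three of 25 takes the false-claim rate from the nominal 5% to between about 8% and 43%. That range rests on assumed failure rates, an assumed excess of 2-4 points, and the plan's SD of 1.1. A reader might go further and conclude that the plan is biased in favour of IPACK. The documents do not establish that, because they do not show in which arm exclusions would fall or how those patients would score.

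**What to change.** - **Primary analysis (12.2 and 17.1).** Analyse all randomised patients in their assigned group, using the observed POD0 pain scores whatever violation or VAS >7 withdrawal occurred. Say that withdrawal does not remove scores already recorded. If recording stops at withdrawal, the recorded maximum is only a lower bound, so state how that will be handled.
- **Supporting analysis.** Add a per-protocol set, with the excluding violations listed in advance and classified by someone who does not know the group.
- **Claim.** Declare non-inferiority only if the one-sided 95% upper limit for IPACK minus control is below 1 point in both sets.
- **Reconcile 6.5 and 14.1.** Both name femoral and sciatic failures only. The sponsor must settle whether the VAS >7 rule covers the IPACK arm, and how it fits with maximal POD0 pain as the outcome the trial is powered on.

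The cost in text is a few sentences and one extra analysis, with no change to recruitment. The statistical cost can be more than a slightly wider interval. Retained failures raise both the IPACK mean and its variance, with the power losses shown in the working, and requiring agreement of two analyses cannot raise power. The sponsor should state the failure rate it expects and check whether 50 patients still suffice.
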